**Study Procedures:** We will assess the patient's pain in a standardized fashion using the FPS-R, administered in the patient's primary language. We will assess the FPS-R and vNRS at baseline (within 15 minutes prior to receiving the study drug) and then at 10 minutes, 30 minutes, and 60 minutes (or within 5 minutes of each mark to allow for unpredictable setting of the emergency department) after administration of the study drug for 60 minutes. We will assess pain associated with nasal administration using the same two scales within 15 minutes of study drug administration. The patient will then be assessed at 2 hours (or within 10 minutes) after administration of the study drug and at 24 hours after study drug administration. Pain assessment not required if a valid documented reason is provided. Such reasons may include, but are not limited to: patient is asleep, having a procedure done, or other medically indicated reason that prohibits a pain assessment from being performed. The Data Collection Form will serve as source document for study drug administration time. The Study Physician will sign on the Data Collection Form as a witness.

If the 24-hour mark is during a timeframe that is inconvenient for the patient (e.g. during sleeping hours), the assessment will be made at a point greater than, but as close to as possible to, the 24-hour mark, within 48-hours of study drug administration. We will conduct the 24-hour follow up by telephone if the patient is discharged from the ED, or in person if the patient is hospitalized (the decision to hospitalize will not be dictated by the study). Patients will be reimbursed \$10 for the time and effort spent participating in this study.

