**Outcomes: Primary Aim:** To demonstrate that IN ketorolac is non-inferior to IV ketorolac in reducing pain in children with acute migraine headaches, we will compare the mean decrease in pain score of both study groups at 60 minutes after administration of the study drug to each other. The outcome we will use to measure this decrease in pain will be the Faces Pain Scale – Revised (FPS-R). The FPS-R is a 10 point pain scale that has been validated for the use in children greater than 4 years of age in the ED; is one of the self-report measures of pain recommended for research in children; and is commonly used as the primary outcome in ED research.(56,57) IN ketorolac will be considered non-inferior to IV ketorolac if the difference between the mean decreases in pain score of both groups is less than a clinically meaningful difference in pain. The minimum clinically meaningful difference in pain in children when using the FPSR has been shown to be 2 out of 10, and is consistent across all categories of age, sex, ethnicity, and primary language; (58) therefore, the non-inferiority margin (delta) will be set at 2/10. In addition to the FPS-R, we will also assess pain using a descriptive ordinal scale frequently used in headache research.(59) Using this scale, we will ask the patient to describe their headache pain as severe, moderate, mild, or none. We will also use the verbal numeric rating scale (vNRS), which involves asking the patient how much pain they have on a scale from zero to ten. We selected the reduction in pain, rather than pain freedom as recommended by the IHS guidelines, as pain freedom is very seldom achieved in the ED, with only approximately 20% of patients reportedly being pain free upon discharge. (59-61) Prior comparative trials of abortive migraine and headache therapies in the ED have similarly shown that as few as 15% of adults and 7% of children achieve headache freedom after treatment, but greater than 60% experience headache relief.(40,62) As a result, pain freedom from migraine or headaches has been infrequently used as the primary outcome for studies in the ED setting; instead, degree of pain relief has been used.(37-40,63-66) Additionally, we chose the one hour end point based on the IHS recommendations that a time point earlier than two hours should be considered for parenteral study medications (which would apply to both IV and IN routes).(59)

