### **Statistical Procedures:**

We will enroll 80 children (40 in each group) ages 8 to 18 years. We based our sample size on the ability to demonstrate non-inferiority between the IN and IV ketorolac groups' ability to reduce pain. It has been shown that a reduction of 2 on the FPS-R score is the minimum clinically significant difference in pain in children. Therefore, our predetermined margin of non-inferiority is 2. In order to be conservative for the sample size calculation, we based the calculation on a margin of 10% less than our predetermined margin of non-inferiority of 2. The resulting sample size of 80 children, therefore, is based on a margin of 1.8 on the FPS-R pain scale. Using a standard deviation of 2.725 (again, selected using conservative assumptions), a sample size of 40 patients per group provides 90% power to detect non-inferiority using a one-sided two sample t-test with an alpha of 0.05.

We will conduct an intention to treat analysis for all enrolled randomized subjects. We will conduct a one-sided t-test to evaluate the difference between the mean decreases in pain score of the two study groups (primary outcome). The difference between groups, with its 95% CI, will be compared to the pre-determined non-inferiority margin (i.e. 2/10) to establish whether IN ketorolac is noninferior to IV ketorolac. For our secondary outcome (time to clinically significant reduction in pain), we will also compare groups using a two-sample one-

sided t-test. Similar to the analysis for the primary outcome, the difference between groups in the time to clinically significant reduction in pain, with its 95% CI, will be compared to the pre-determined non-inferiority margin of 10 minutes. A Kaplan-Meier distribution analysis will also be used to compare the time to meaningful pain relief in the two treatment groups. For other secondary outcomes, we will compare groups using standard bivariate analyses for categorical and continuous variables and a table describing adverse events by treatment will be reported.

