### **Potential Risks:**

There are no risks in addition to the usual risks associated with receiving ketorolac for analgesia. There is a chance that a patient may not experience the same degree of pain relief that they may have experienced if they had received IV ketorolac. However, patients will have their pain assessed as per usual standard care, and can receive any additional required analgesics at any point in time if their pain relief is inadequate. The procedures involved in this study do not increase the risk for adverse events normally associated with receiving ketorolac.

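### The primary 60-minute pain score may be omitted for reasons such as sleep, but the analysis plan has no rule for unscored children and no sensitivity analysis

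*Combined protocol and SAP*

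**What the plan says.** Three parts of the combined protocol and SAP have to be read together.

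- **Study Procedures (under Study Design).** FPS-R is scheduled at baseline, 10, 30 and 60 minutes (each within 5 minutes), then at 2 hours and 24 hours. A general waiver follows: "Pain assessment not required if a valid documented reason is provided". The examples are an open list: "Such reasons may include, but are not limited to: patient is asleep, having a procedure done", ending with other medical reasons that prevent an assessment. The waiver comes after the 2-hour and 24-hour sentence, but nothing in its wording limits it to those times.
- **Outcomes, Primary Aim.** The primary endpoint is fixed at one time point: "we will compare the mean decrease in pain score of both study groups at 60 minutes after administration of the study drug". The margin is 2 on the FPS-R.
- **Statistical Procedures.** The population is stated as follows: "We will conduct an intention to treat analysis for all enrolled randomized subjects". The method is: "We will conduct a one-sided t-test to evaluate the difference between the mean decreases in pain score of the two study groups". The decision step is: "The difference between groups, with its 95% CI, will be compared to the pre-determined non-inferiority margin (i.e. 2/10". The test is one-sided at 0.05. The CI is called 95% without saying whether it is one-sided or two-sided.

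No section says how a child without a 60-minute score enters the primary comparison. None plans a sensitivity analysis or allows for missing scores in the 80 children.

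**The concern.** The promise to analyse every randomised child and the named method do not meet. A two-sample t-test uses only children who have a 60-minute decrease. Unless scores are imputed first, which the plan does not mention, the analysis becomes one of scored children only.

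The reason for absence may also carry information. A child asleep at 60 minutes may have had more relief than average, or may differ in some other way. If the unscored share or the relief gap differs between arms, the IV-minus-IN difference is shifted. A shift toward zero favours a finding of non-inferiority; a shift the other way works against it. Blinding of patients and pain assessors (Study Design) limits differences driven by staff behaviour, but not differences caused by the drugs themselves.

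With no rule in place, the handling could also be chosen after the pattern of missing scores is known.

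**Working it through.** **Inputs from Statistical Procedures:** 40 per arm, SD 2.725, margin 2 (1.8 for sample size), one-sided alpha 0.05. **Assumed:** a true difference of 0 for power, and every missing-score rate and relief gap. Differences are IV minus IN in mean decrease, so positive values mean IN is worse. Results are given for the one-sided 0.05 test and for a two-sided 95% CI (2.5% in the relevant tail), because the plan's wording admits both.

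**1. The plan's own figure.** SE = 2.725 × √(2/40) = 0.609. With margin 1.8 and one-sided 0.05, noncentral-t power is 90.0%. The stated 40 per arm for 90% is reproduced, with no allowance for missing scores.

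**2. How a bias arises.** If q is the share unscored in an arm and D is how much larger the mean decrease is in unscored than in scored children, the scored-only analysis understates the IV advantage by D × (qIV − qIN). With qIV = 15% and qIN = 5%, D = 1 gives 0.1 and D = 2 gives 0.2. Swapping the arms reverses the sign. Equal rates and equal D give 0.

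**3. Error at a true deficit of 2, with 36 scored per arm.** SE = 2.725 × √(2/36) = 0.642; noncentrality = bias/SE.

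| Bias toward non-inferiority | One-sided 0.05 | Two-sided 95% CI |
|---|---|---|
| −0.2 | 2.5% | 1.2% |
| −0.1 | 3.6% | 1.7% |
| 0 | 5.0% | 2.5% |
| +0.1 | 6.8% | 3.5% |
| +0.2 | 9.1% | 4.9% |

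**4. Same mechanism in both arms.** Suppose being unscored depends on the child's own 60-minute decrease through a logistic curve, identical in both arms, with 10% unscored on average and mean decreases of 4 (IV) and 2 (IN). A slope of 0.25 per point gives 12.1% and 7.9% unscored and a bias of 0.07; a slope of 0.40 gives 13.1% and 6.9% and a bias of 0.15. Both biases are toward non-inferiority, and they are the same size if the slope is negative. If the drugs are equal, the bias is 0.

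**5. Tipping point.** Let n be scored and m = 40 − n unscored per arm, d the observed difference, and G the extra improvement of unscored IV over unscored IN children. The full-set difference is (n × d + m × G)/40. With the SE taken from scored children, non-inferiority is lost when G = [(2 − t × SE) × 40 − n × d]/m.

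- m = 4: t × SE = 1.667 × 0.642 = 1.071 (one-sided) or 1.994 × 0.642 = 1.281 (two-sided). At d = 0 this gives 0.929 × 40/4 = 9.3, or 0.719 × 40/4 = 7.2.
- m = 8: SE = 0.681; t × SE = 1.138 or 1.362.

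| Unscored per arm | d | G, one-sided 0.05 | G, two-sided 95% CI |
|---|---|---|---|
| 4 | 0 | 9.3 | 7.2 |
| 4 | 0.5 | 4.8 | 2.7 |
| 4 | 0.75 | 2.5 | 0.4 |
| 8 | 0 | 4.3 | 3.2 |
| 8 | 0.5 | 2.3 | 1.2 |
| 8 | 0.75 | 1.3 | 0.2 |

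**6. Power, equal drugs, margin 2.** With 40, 36 and 33 scored per arm: 94.6%, 92.5% and 90.4% one-sided, or 90.0%, 86.7% and 83.6% with a two-sided CI.

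**7. What a model recovers.** In a simulation with assumed means and correlations (10,000 trials per case), the stronger logistic case left a t-test bias of about 0.15. A baseline-adjusted repeated-measures model cut it to 0.05–0.10 when only the 60-minute score was missing, and to 0.11–0.15 when only the 10-minute score remained. When sleep depended on the observed 30-minute score, the t-test bias was 0.02–0.04 and the model's at most 0.02.

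**The case against.** - **The waiver is not a free choice.** It needs a valid recorded reason, a 5-minute window is allowed, and patients and assessors are blinded. A reader might infer that staff can skip scores at will; the text does not say so. This stands, but it does not address missingness caused by drug effect.
- **Exclusion is an inference.** The plan never says unscored children are dropped, and a t-test can follow imputation. This stands too: the fault is that no rule is stated. A t-test at one prespecified time point is not wrong in itself.
- **The sizes are hypothetical and often small.** A bias of 0.07–0.15 is about 4–8% of the margin. With 4 unscored per arm and no observed difference, reversal needs a gap of 9.3 points on a 10-point scale (7.2 under a two-sided CI). This stands, and limits the point to results near the margin or many missing scores.
- **A repeated-measures model is not clearly better.** Step 7 shows only partial correction when missingness depends on the unseen score. So the documents give no ground for insisting on that model, and imputation followed by the planned comparison serves as well.
- **Scores after additional analgesics are another matter.** Potential Risks says patients "can receive any additional required analgesics at any point in time if their pain relief is inadequate". Using scores as observed is a natural intention-to-treat reading. The point is separate and secondary.

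**Conclusion.** The concern holds as a gap in the analysis plan: the primary score may be absent for reasons that could be linked to relief, every randomised child is to be analysed, and neither a rule for the unscored child nor a sensitivity analysis connects the two. It should be corrected, but nothing shows that it invalidates the trial.

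A reader might infer that the analysis is biased in favour of IN ketorolac. The documents do not support that. They give no missing-score rates, the bias can run either way, and it is zero when rates and relief gaps are equal. Nor can one say in general that error exceeds 5%: for biases of 0.1 and 0.2 it does under the one-sided 0.05 test (6.8% and 9.1%) but not under a two-sided 95% CI (3.5% and 4.9%). Whether the loss of power is minor also depends on that reading: 90.4% against 83.6% with 33 scored per arm.

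All sizes rest on the plan's SD of 2.725 and on assumed missingness. Confidence is medium.

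**What to change.** Amend Statistical Procedures before unblinding.

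1. **Primary analysis.** Keep the 60-minute comparison with the margin of 2, but include all randomised children. Use multiple imputation within arm from the baseline, 10-, 30- and 120-minute FPS-R, followed by the planned comparison adjusted for baseline FPS-R. An equivalent alternative is a baseline-adjusted repeated-measures model with the 60-minute contrast. State how a child with no post-baseline score is handled.
2. **Sensitivity analysis.** Vary the assumed 60-minute decrease of unscored children separately by arm until the conclusion changes. Do not make this the decision rule. If 10% per arm were unscored, with unscored IV children improving by 4 to 6 points and unscored IN children by none, the shift would be 0.10 × 4 = 0.4 to 0.10 × 6 = 0.6. Power for equal drugs (margin 2, one-sided 0.05, 40 per arm) would then fall from 94.6% to 83%–74%.
3. **Reporting.** Tabulate unscored children by arm and reason, using the reasons already recorded.
4. **Separately,** state how scores taken after additional analgesics are used in the analysis. This asks for an analysis convention only, not a change in care.

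The cost is a little more analysis work, with no extra patients or assessments. The main estimate would rely on missing at random, so bias is only partly removed if missingness depends on the unseen score. That is why the tipping-point analysis is needed.

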Secondary Aim: To determine if there is a difference in time to achieve a clinically significant reduction in pain after receiving IN ketorolac compared to IV ketorolac, we will use the outcome of time (in minutes) and compare, as appropriate, the mean or median time it takes after administration of study drug in each group to achieve a minimum clinically significant difference in pain (i.e. 2/10 on the FPS-R).

Note that a prior iteration of the protocol stated that this secondary aim was to determine if IN ketorolac was non-inferior to IV ketorolac, with a non-inferiority margin for this aim of 10 minutes. This secondary aim was changed prior to starting patient enrollment (i.e. no patients were enrolled yet) because the number of pain assessments was decreased from assessments at 10, 20, 30, 40, 50, 60, and 120 minutes to 10, 30, 60, and 120 minutes for feasibility reasons. Since we would then no longer be able to assess change in pain score in 10 minute increments, it would not have been possible to accurately assess for non-inferiority based on a non-inferiority margin of 10 minutes. Therefore, the aim was changed to as is currently stated.

Additional efficacy outcomes will include those that are ED-based, and those assessed at a 24- hour follow up:

- i) ED-based outcomes: 1) Receipt of rescue medications at any time during the ED visit; 2) Headache relief in the ED, defined as change within 2 hours of the patient's description of headache from severe or moderate to either mild or none, on the severe/moderate/mild/none pain scale, without the use of rescue medications; 3) Headache freedom in the ED, defined as achieving a headache level of none within 2 hours without the use of rescue medications; and 4) Percentage improvement in pain score between baseline and one hour, defined as (baseline pain score – one hour pain score)/baseline pain score.

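### The t-test on minutes to a 2-point FPS-R drop gives no value to children who never achieve it, and the planned Kaplan-Meier analysis that could keep them is only an unspecified addition

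*Combined protocol and SAP*

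**What the plan says.** The Secondary Aim paragraph under Outcomes takes time in minutes as the outcome and compares, whichever is appropriate, "the mean or median time it takes after administration of study drug in each group to achieve a minimum clinically significant difference in pain", set at 2/10 on the FPS-R. It does not say what happens to a child who never reaches that drop.

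The same section records that the assessments were reduced from "10, 20, 30, 40, 50, 60, and 120 minutes to 10, 30, 60, and 120 minutes for feasibility reasons". Study Procedures adds: "The patient will then be assessed at 2 hours (or within 10 minutes) after administration of the study drug and at 24 hours". The 24-hour contact may slip to 48 hours. Individual scores may be missed: "Pain assessment not required if a valid documented reason is provided". Under Potential Risks, children "can receive any additional required analgesics at any point in time if their pain relief is inadequate".

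Statistical Procedures states an intention-to-treat analysis of all enrolled randomised subjects. For the time outcome it says "we will also compare groups using a two-sample one"-sided t-test, with a 95% CI. It then adds: "A Kaplan-Meier distribution analysis will also be used to compare the time to meaningful pain relief in the two treatment groups". It gives no order of precedence between the two analyses.

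**The concern.** A t-test needs a number of minutes for every child analysed, and a child without the drop at 120 minutes has none. If such children are left out, the groups compared are chosen after randomisation by the effect under study. A mean among achievers measures how fast relief came to those who got it and says nothing about how many got it.

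The secondary hypothesis is that time to relief does not differ between routes. Suppose the intranasal route helped fewer children but just as quickly. An achievers-only comparison would then tend to show no difference, which agrees with the hypothesis. If a time is assigned instead, the result depends on a value the plan does not fix, so it could be chosen after the data are seen.

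**Working it through.** **The plan's own figure.** The only sample size stated is for the primary outcome: margin 1.8, SD 2.725, one-sided alpha 0.05, power 90%.

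n per arm = 2 × (1.645 + 1.282)² × 2.725² / 1.8² ≈ 39.3, rounded up to 40.

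This reproduces the plan (power 90.0% by the noncentral t). The present point does not affect it. No power is stated for the time outcome.

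**How many children could lack a time.** The documents give no rate for a 2-point FPS-R drop. The nearest figure, in the Primary Aim paragraph, is headache relief in more than 60% of patients in earlier ED trials, which is a different endpoint. Taking 60% to 90% as an assumed range, 80 × 0.40 = 32 down to 80 × 0.10 = 8 children would have no time.

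**What the t-test can do with them.**
- Exclude them: selection on the outcome, and not intention to treat.
- Assign 120 minutes: each such child contributes 120/40 = 3 minutes to an arm's mean.
- Use the 24-hour contact: each contributes at least 1,440/40 = 36 minutes, so one child could dominate the comparison.

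The plan chooses none of these.

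**Illustration (all rates assumed).** 40 per arm; 80% of IV and 55% of IN children achieve the drop by 120 minutes. Achievers in both arms are split 25/35/25/15% over 10/30/60/120 minutes.

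- Mean among achievers, both arms: 0.25×10 + 0.35×30 + 0.25×60 + 0.15×120 = 46 minutes.
- Children without a time: 40 × 0.20 = 8 (IV) and 40 × 0.45 = 18 (IN).
- Cumulative share of randomised children at 10/30/60/120 minutes: IV 20/48/68/80%, IN 14/33/47/55%.
- Kaplan-Meier median: 60 minutes (IV), 120 minutes (IN).
- Mean time restricted to 120 minutes: 0.80×46 + 0.20×120 = 60.8 (IV); 0.55×46 + 0.45×120 = 79.3 (IN). The difference is 18.5 minutes, against 0 among achievers.

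Rejection rates by simulation, two-sided 5% tests:

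| Achieving the drop | Achievers-only t-test | t-test, non-achievers set to 120 min | Log-rank, censored at 120 min |
|---|---|---|---|
| 80% vs 55% | about 5% | about 46% | about 64% |
| 80% vs 60% | about 5% | not tabulated | about 46% |
| 80% vs 70% | about 5% | not tabulated | about 15 to 16% |

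With equal timing among achievers, the achievers-only test stays at its nominal error rate whatever the gap in response.

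**What the Kaplan-Meier sentence leaves open.** It names no between-group test and no censoring time. It does not tie its relief event to the 2-point FPS-R drop. It does not say how skipped scores, or scores after additional analgesics, enter the analysis. The neighbouring headache-relief and headache-freedom outcomes do exclude rescue medication; the time outcome is silent.

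**The case against.** A reader might infer that the secondary comparison covers responders only and cannot answer its aim. The documents do not support that:
- Nothing restricts the time outcome to achievers, and Statistical Procedures states intention to treat. On non-achievers the plan is silent, which is not the same as excluding them.
- A Kaplan-Meier comparison of the two groups is pre-specified and can keep non-achievers as censored. In the illustration above it would show medians of 60 and 120 minutes.
- The Secondary Aim paragraph allows a median as well as a mean. A median can be estimated with non-achievers included if at least half of each group achieves the drop.

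A lower response share would also bear on other planned outcomes: the primary FPS-R decrease at 60 minutes, headache relief and freedom within 2 hours, and rescue use. The 80% versus 55% split is a large assumed gap. At 80% versus 70% even the log-rank test has little power with 80 children.

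All of this stands, and it narrows the point without removing it. The t-test is still the first analysis named for this outcome and still lacks a value for non-achievers. The intention-to-treat statement makes leaving them out inconsistent but does not supply a value. The Kaplan-Meier analysis is too loosely specified to settle a disagreement between the two.

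**Conclusion.** The point holds as a specification gap in a secondary outcome that should be closed. As written, the t-test on minutes either conditions on a post-randomisation outcome or depends on an unstated assigned time, and nothing says whether it or the Kaplan-Meier analysis decides.

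The size depends on response rates that the documents do not give. Under the assumed rates and equal timing among achievers, the loss from an achievers-only test is large for a 25-point gap in response (about 5% against 64% rejection) and modest for a 10-point gap (about 5% against 15 to 16%). The mechanism itself needs only that some children do not achieve the drop by 120 minutes. The primary outcome and its sample size are unaffected. The conclusion does not rely on the 10-minute margin or on the sidedness of the test, which are a separate matter.

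**What to change.** In the Secondary Aim paragraph and in Statistical Procedures:

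1. Make the time-to-event comparison in all randomised children the analysis of this aim.
2. Define the event as the first 2-point FPS-R drop from baseline, and censor children who have not achieved it at their last ED score.
3. Name a between-group test suited to the 10/30/60/120-minute grid, such as a log-rank test with handling of ties or an interval-censored version.
4. State how skipped scores, and scores after additional analgesics, are treated in this analysis.
5. Report the proportion of randomised children achieving the drop by 10, 30, 60 and 120 minutes, with CIs.
6. Drop the t-test on mean time, or label it descriptive among achievers.

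The cost is wording in two places and no new data. The small downside is losing a single mean-minutes headline.

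### Time to pain relief is summarised in minutes from readings at only 10, 30, 60 and 120 minutes, so recorded medians, absolute times and the Kaplan-Meier median are largely set by the visit grid.

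*Combined protocol and SAP*

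**What the plan says.** Under Outcomes, Secondary Aim, the plan states "we will use the outcome of time (in minutes) and compare, as appropriate, the mean or median time it takes" in each group "to achieve a minimum clinically significant difference in pain (i.e. 2/10 on the FPS-R"). The same section explains that the readings were "decreased from assessments at 10, 20, 30, 40, 50, 60, and 120 minutes to 10, 30, 60, and 120 minutes" for feasibility, before any child was enrolled. It concedes that a 10-minute non-inferiority margin could not be judged accurately on the thinner schedule, and it changes the aim to a question of difference.

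Study Procedures sets the readings "and then at 10 minutes, 30 minutes, and 60 minutes (or within 5 minutes of each mark"), and adds "The patient will then be assessed at 2 hours (or within 10 minutes) after administration of the study drug". A reading may be skipped for a documented reason, such as sleep or a procedure.

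Statistical Procedures tests this outcome with a one-sided two-sample t-test and compares the difference and its 95% CI with a 10-minute non-inferiority margin. It then adds: "A Kaplan-Meier distribution analysis will also be used to compare the time to meaningful pain relief in the two treatment groups". Neither section names a method for interval-censored or grouped times. Neither says what time is given to a child relieved between readings, or how a child never relieved enters the t-test.

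**The concern.** A child who reaches the 2-point drop is known only to have done so between two readings. Those intervals are 10, 20, 30 and 60 minutes wide, and wider still after a skipped reading. Taking the reading time as the event time rounds every relief time up to the next mark. A median, an average time quoted for one arm, or a Kaplan-Meier median then says more about when staff looked than about when pain eased.

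This is the only named secondary aim, and its hypothesis is that the groups do not differ. Recorded medians of 60 and 60 could be read as confirming that hypothesis when the true medians are far apart, and 30 against 60 could be read as a large difference when they nearly coincide. The median is one of the two summaries the plan allows.

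**Working it through.** **Inputs.** From the plan: marks at 10, 30, 60 and 120 minutes; windows of ±5 minutes (±10 at 2 hours); 40 children per arm. The plan gives no distribution of relief times, so exponential, Weibull and lognormal shapes are assumed, and children unrelieved at 120 minutes are set to 120.

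**The plan's own figure.** None is given for this outcome. The stated sample size concerns FPS-R at 60 minutes and reproduces: 2 × (1.645 + 1.282)² × 2.725² / 1.8² = 39.3, so 40 per arm.

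**1. Medians.** The recorded median is the first mark *t* at which the proportion relieved, F(t), reaches one half. For exponential times with median *m*, F(t) = 1 − 2^(−t/m).
- *m* = 28: F(30) = 0.524, recorded 30. *m* = 32: F(30) = 0.478 and F(60) = 0.727, recorded 60. A true gap of 4 becomes 30.
- *m* = 32 v 58: for 58, F(30) = 0.301 and F(60) = 0.512. Both record 60, so a true gap of 26 becomes 0.
- *m* = 55 v 65: F(60) = 0.531 and 0.473, recorded 60 and 120. A true gap of 10 becomes 60.

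Lognormal times with log-SD 0.5 or 0.8 give the same recorded medians, because any population median is rounded up to the next mark.

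**2. Chance differences between identical arms.** With a true median of 30, the number X relieved by 30 minutes in an arm of 40 is binomial(40, 0.5). Ignoring the small chance of other marks, the sample median reads 30 if X ≥ 21, 45 if X = 20, and 60 if X ≤ 19. P(X = 20) = 0.125, so each of the other two has probability (1 − 0.125)/2 = 0.437. The chance that one arm reads 30 and the other 60 is 2 × 0.437² = 0.382. Simulation gives 38% for a difference of 20 minutes or more (39% with visit windows). With exact times it is 4% (exponential) or under 1% (lognormal). The figure depends on where the median lies. For exponential times it is 4.7% against 0.3% at a true median of 20, and 22.5% against 12.2% at 40.

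**3. Absolute means.** With S = 1 − F, the recorded mean capped at 120 minutes is 10 + 20·S(10) + 30·S(30) + 60·S(60). For an exponential median of 30 this is 10 + 20 × 0.794 + 30 × 0.5 + 60 × 0.25 = 55.9. The true capped mean is (30/ln 2) × (1 − 2^(−4)) = 40.6, an excess of 15.3 minutes. Across the exponential and lognormal cases the excess is about 12 to 22 minutes per arm.

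**4. Mean differences and the t-test.** With equal arms, the two-sided t-test rejects in 4 to 6% of simulated trials. Real differences are distorted by an amount that depends on shape. Exponential cases barely move (11.0 recorded as 11.7; 22.7 as 21.5), while the Weibull cases run from 6.7 recorded as 6.0 (−10%) to 20.2 recorded as 30.2 (+50%). The lognormal cases run from about −6% to +30%. In the exponential cases, power fell from 82% to 76% and from 50% to 42%.

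**5. Kaplan-Meier.** At nominal times the curve steps only at the four marks. Its values there are the observed proportions relieved and are valid. Its median and its shape between marks come from the grid.

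**6. Consistency.** The Secondary Aim text drops the 10-minute margin as not accurately assessable on this schedule. Statistical Procedures still applies that margin, with a one-sided test.

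**The case against.** The strongest reply is that both arms share one grid, and patients and pain assessors are blinded, so rounding cannot create a mean difference where none exists. That is correct. The t-test is the named test, and it does not lose sight of a large effect: for lognormal medians of 32 v 58, which both record as 60, the grid t-test rejects in 99.6% of trials at log-SD 0.5 and 84% at log-SD 0.8. A reader might infer that differences in mean minutes are also mostly grid artefact, or that the t-test is invalid. Neither follows.

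A reader might also infer that the windows make Kaplan-Meier rank children by when the assessor arrived. That holds only if actual rather than nominal times are analysed, and the plan does not say which.

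The protocol does acknowledge the coarse schedule, and choosing mean or median as appropriate leaves some latitude. But the acknowledgement is used only to drop the margin. The outcome in minutes stays, and Statistical Procedures was not brought into line.

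**Conclusion.** The concern holds in a limited form. Median differences, absolute times, and the Kaplan-Meier median and between-reading shape are largely set by the reading schedule. The t-test on mean differences keeps about 5% type I error with modest power loss, and Kaplan-Meier at the nominal marks is sound.

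That recorded medians fall on the marks (or midway between two, in an even-sized arm) follows from the schedule alone. The 38% figure further assumes that both true medians lie at 30 minutes, and the excess in means and the distortion of mean differences rest on assumed relief-time distributions. Separately, the Secondary Aim text and Statistical Procedures contradict each other on the margin and the direction of the test. This is a secondary outcome; the primary comparison at 60 minutes and the sample size do not depend on it.

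**What to change.** In Outcomes (Secondary Aim) and Statistical Procedures, replace mean or median minutes and the t-test with:
- the cumulative proportion in each arm with a 2-point or larger FPS-R drop by 10, 30, 60 and 120 minutes, with risk differences and 95% CIs;
- one pre-specified comparison suited to the data, either a discrete-time complementary log-log model or an interval-censored log-rank test, in which a skipped reading widens that child's interval.

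Reconcile the two sections by removing the one-sided test and the 10-minute non-inferiority margin for this outcome.

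As an illustration of what respecting the intervals gains, an interval-censored Weibull fit to simulated exponential data (40 per arm, true medians 25 v 35) estimated the 10-minute difference as 9.7 on average (SD 8.3). The difference in raw recorded medians averaged 15.9 (SD 17.2).

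The cost is wording only, with no new data. The result is no longer a single number of minutes.
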